#### 9.1.5. Extension Phase

After Week 96 subjects will be given the opportunity to continue D/C/F/TAF treatment during an extension phase until the D/C/F/TAF FDC tablet becomes commercially available and is reimbursed, or can be accessed through another source in the country where he/she is living, or until the sponsor terminates clinical development. During the extension phase subjects will

attend visits every 6 months thereafter. The time window during the extension phase is  $\pm 14$  days of the protocol-specified visit date. The following evaluations are to be completed and documented at each visit.

- Review of AEs and changes in concomitant medications.
- Symptom-directed physical examination (physical examination of body parts for which symptoms have been reported by the subject) as needed.
- Vital signs measurement (blood pressure and pulse) and weight.
- Midstream urine sample collection for the following laboratory procedures:
  - Urinalysis and urine chemistry (see also Section 9.1.2.1).
  - Urine pregnancy test (females of childbearing potential only); positive urine pregnancy tests will be confirmed with a serum test; if this test is positive, the subject will be withdrawn (see also Section 12.4.3).
- Blood sample collection for the following laboratory analyses:
  - Chemistry profile (see also Section 9.1.2.1).
  - Hematology profile (see also Section 9.1.2.1).
  - eGFRcreatinine according to the Cockcroft-Gault formula, and the CKD-EPI formula (for details, see Section 9.5.4).
  - Plasma HIV-1 RNA.
  - CD4+ cell count.
  - HIV-1 resistance testing. HIV-1 PR/RT genotype/phenotype testing will be requested by the study virologist on samples from subjects eligible for resistance testing.
- Document study drug dispensation and accountability for all study drugs dispensed.

#### 9.1.6. Post-treatment Phase

## 9.1.6.1. Early Study Treatment Discontinuation Visit

Subjects who prematurely discontinue, either during the double-blind treatment phase (from Day 1 to Week 48) or during the open-label single-arm treatment phase (between Week 48 and Week 96) will be required to return to the clinic within 72 hours of stopping study treatment for the ESTD visit.

Any evaluations at the ESTD visit showing abnormal results indicating that there is a possible or probable causal relationship with study drug, need to be followed (as often as deemed prudent by the investigator) until satisfactory clinical resolution or stabilization.

The following procedures are to be completed and documented.

- Review of AEs and changes in concomitant medications.
- Complete physical examination (urogenital/anorectal examinations will be performed at the discretion of the investigator).
- Vital signs measurement (blood pressure and pulse) and weight.
- Midstream urine sample collection for the following laboratory procedures:
  - Urinalysis and urine chemistry (see also Section 9.1.2.1).
  - Urine renal biomarkers: required if the last test was more than 12 weeks before the ESTD visit (fasted, ie, no food or drinks, except water, at least 8 hours prior to urine collection; if the subject has not fasted prior to the visit, the visit may proceed, but the subject must return within 72 hours in a fasted state to provide a urine sample for renal biomarkers) (see also Section 9.1.2.2).
  - Urine pregnancy test (females of childbearing potential only); positive urine pregnancy tests will be confirmed with a serum test. If the test is positive, see Section 12.4.3 for the procedure to follow.
- Blood sample collection for the following laboratory analyses:
  - Chemistry profile (see also Section 9.1.2.1).
  - Hematology profile (see also Section 9.1.2.1).
  - eGFRcreatinine according to the Cockcroft-Gault formula, and the CKD-EPI formula (for details, see Section 9.5.4).
  - Plasma HIV-1 RNA.
  - CD4+ cell count.
  - HIV-1 resistance testing. HIV-1 PR/RT genotype/phenotype testing will be requested by the study virologist on samples from subjects eligible for resistance testing.
  - Plasma storage sample for possible additional clinical testing.
  - PBMC storage sample for exploratory analysis (eg, to characterize archived viral resistance) if deemed necessary by the study virologist.
- Pharmacokinetic blood sample.
- Document study drug accountability for all study drugs dispensed.

In subjects participating in the bone investigation substudy:

• Bone biomarkers (collected fasted, ie, no food or drinks, except water, at least 8 hours prior to sample collection): CTX, P1NP, PTH and 25-hydroxy vitamin D. If the subject has not fasted prior to the visit, the visit may proceed but the subject must return within 72 hours in a fasted state to provide a blood sample for bone biomarker assessment.

• DXA scan of spine and hip: only to be performed at ESTD (±2 Weeks) if the last scan is more than 12 weeks from the date of the ESTD visit and the ESTD visit takes place before Week 96. A rescan for technical reasons within 4 weeks is allowed.

# 9.1.6.2. 30-Day Follow-up Visit

A 30-day FU visit will be required for any subject who has an ongoing AE or SAE at the time of his/her last study visit (unless consent is withdrawn).

A time window of  $\pm 7$  days of the protocol-specified visit date may be used for this 30-day FU visit. The following evaluations are to be completed and documented.

- Review of AEs and changes in concomitant medications.
- Symptom-directed physical examination (physical examination for which symptoms have been reported by the subject) as needed.
- Weight.
- Midstream urine sample collection for the following laboratory procedures:
  - Urinalysis and urine chemistry (see also Section 9.1.2.1).
  - Urine pregnancy test (females of childbearing potential only); positive urine pregnancy tests will be confirmed with a serum test. If the test is positive, see Section 12.4.3 for the procedure to follow.
- Blood sample collection for the following laboratory analyses:
  - Chemistry profile (see also Section 9.1.2.1).
  - Hematology profile (see also Section 9.1.2.1).
  - eGFRcreatinine according to the Cockcroft-Gault formula, and the CKD-EPI formula (for details, see Section 9.5.4).
  - Plasma HIV-1 RNA.
  - CD4+ cell count.

## 9.2. Efficacy Evaluations

# 9.2.1. Antiviral Efficacy and Immunologic Change

Samples for determination of plasma HIV-1 RNA viral load and immunologic parameters will be taken at the time points specified in the Time and Event Schedule.

Plasma viral load levels will be measured using a validated assay, which will be conducted by the central laboratory.

Immunologic change will be determined by changes in CD4+ cell count (absolute and %).

Changes in viral load, changes in CD4+ cell counts (either decreases or increases), or detected resistance will be part of the efficacy analysis and should not be reported as (S)AE.

#### 9.2.2. Resistance Determinations

Samples for HIV-1 genotype/phenotype resistance testing, as well as a PBMC sample will be taken at the time points specified in the Time and Event Schedule. PBMC samples will be taken for storage for exploratory analysis (eg, to characterize archived viral resistance) only if deemed necessary by the study virologist.

### 9.2.2.1. Virologic Failure

Subjects who are on study medication and who experience a protocol defined confirmed VF, ie, virologic nonresponse (NR) or virologic rebound (RB), as defined below, will be considered to have VF for the purpose of the resistance analysis.

### **Virologic Nonresponse:**

• HIV-1 RNA <1 log10 reduction from baseline and ≥50 copies/mL at the Week 8 visit, confirmed at the following scheduled or unscheduled visit following Week 8.

Subjects (and the resistance testing on samples from these subjects), who meet the criteria for NR will be managed according to the protocol schema provided in Figure 2.

## **Virologic Rebound:**

- At any visit, after achieving confirmed (consecutive) HIV-1 RNA <50 copies/mL, a rebound in HIV-1 RNA to ≥50 copies/mL, which is subsequently confirmed at the following scheduled or unscheduled visit; or
- At any visit, a  $>1 \log_{10}$  increase in HIV-1 RNA from the nadir which is subsequently confirmed at the following scheduled or unscheduled visit.

Subjects (and the resistance testing on samples from these subjects), meeting the criteria for RB will be managed according to the schema provided in Figure 3.

# 9.2.2.2. Subjects Eligible for Resistance Testing

To investigate the emergence of PR/RT resistance, the following subjects will be eligible for genotypic/phenotypic resistance testing:

- Any subject who experiences a protocol defined confirmed VF, ie NR or RB, and has an HIV-1 RNA value ≥400 copies/mL (see Section 9.2.2.1);
- Any subject who discontinues study treatment and has an HIV-1 RNA value ≥400 copies/mL at the last viral load measurement (within 72 hours after discontinuation of the study treatment).

For subjects with confirmed VF (NR or RB), the plasma sample corresponding to the confirmed VF time point will be analyzed if HIV-1 RNA value ≥400 copies/mL. In case of confirmed VF

but with an HIV-1 RNA value <400 copies/mL at the confirmed VF point, resistance testing might then be done at a later time point if HIV-1 RNA value ≥400 copies/mL or at the unconfirmed VF point if HIV-1 RNA value ≥400 copies/mL. In case of persistent low level viremia between 50 and 400 HIV-1 RNA copies/mL, study drugs may be discontinued at the investigator's discretion and the subject will be withdrawn from the study.

An HIV-1 PR/RT genotypic assay will be used to determine the screening genotype for all patients. Further PR/RT genotypic resistance testing will be performed on eligible subjects and phenotypic resistance testing may be done upon request of the study virologist. Baseline phenotyping (and genotyping) may be performed retrospectively on subjects with confirmed VF if they showed evidence of reduced susceptibility after VF to any of the study drugs. Other time points may still be analyzed if deemed necessary by the protocol virologist.

In case of early discontinuation an HIV-1 genotypic resistance report will be forwarded to the investigator in order to assist in the selection of a new ARV regimen.

[figure not shown]
[figure not shown]

Figure 2: Virologic Nonresponse Schema

- a If virologic nonresponse is not confirmed, the subject will remain on its assigned study drug and the subject's viral load will be further monitored.
- b Upon confirmation of virologic nonresponse potential causes should be documented. Assessment should include lack of adherence, concomitant medication, and comorbidities (eg, active substance abuse, depression, or other intercurrent illnesses).
- c If virologic nonresponse is confirmed, the HIV-1 genotype/phenotype (RT and PR) will be analyzed if HIV-1 RNA ≥400 copies/mL.
- d If HIV-1 RNA <400 copies/mL, the subject's viral load will be further monitored and resistance testing may be done at a later time point if HIV-1 RNA ≥400 copies/mL or at the unconfirmed virologic failure point if HIV-1 RNA ≥400 copies/mL. In case of persistent low level viremia between 50 and 400 HIV-1 RNA copies/mL,

- study drugs may be discontinued at the investigator's discretion and the subject will be withdrawn from the study.
- e In case of early discontinuation, an HIV-1 genotypic resistance report, if available, will be forwarded to the investigator in order to assist in the selection of a new ARV regimen.
- Investigators should carefully evaluate the benefits and risks of remaining on study drug for each individual subject and document this assessment in the on-site medical record. Investigators who opt to discontinue study drugs for an individual subject must inform the sponsor's medical monitor prior to study drug discontinuation.

- If virologic rebound is not confirmed, the subject will remain on its current regimen and the subject's viral load will be further monitored.
- Upon confirmation of virologic rebound potential causes should be documented. Assessment should include lack of adherence, concomitant medication, and comorbidities (eg., active substance abuse, depression, or other intercurrent illnesses).
- If virologic rebound is confirmed, the HIV-1 genotype/phenotype (RT and PR) will be analyzed if HIV-1 RNA >400 copies/mL
- If HIV-1 RNA <400 copies/mL, the subject's viral load will be further monitored. In this case of HIV-1 RNA <400 copies/mL at the confirmed virologic failure point, resistance testing may then be done at a later time point if HIV-1 RNA ≥400 copies/mL or at the unconfirmed virologic failure point if HIV-1 RNA ≥400 copies/mL. In case of persistent low level viremia between 50 and 400 HIV-1 RNA copies/mL, study drugs may be discontinued at the investigator's discretion and the subject will be withdrawn from the study.
- In case of early discontinuation, an HIV-1 genotypic resistance report, if available, will be forwarded to the investigator in order to assist in the selection of a new ARV regimen.
- Investigators should carefully evaluate the benefits and risks of remaining on study drug for each individual subject and document this assessment in the on-site medical record. Investigators who opt to discontinue study drugs for an individual subject must inform the sponsor's medical monitor prior to study drug discontinuation.

#### 9.3. Pharmacokinetics Evaluations

#### 9.3.1. Evaluations

Pharmacokinetic assessments (sparse sampling) will be performed for all subjects at the time points specified in the Time and Event Schedule.

In order to distinguish samples from subjects randomized to the D/C/F/TAF treatment arm from those of subjects in the control group, the bioanalytical lab will be unblinded to the treatment groups. However, the sponsor will remain blinded from the origin of the samples that have been analyzed, as well as from the outcome of the analyses, until locking of the database has been performed for the primary analysis.

Single sparse blood samples will be collected at least 30 minutes to maximum 4 hours post-dose on the Weeks 2 through 48 visits, and the ESTD visit (if applicable). At the Weeks 8 and 36 only, 2 blood samples will be collected at 2 time points at least 2.5 hours apart. The first pharmacokinetic sample for the Week 8 and 36 visits should be taken between 1 and 4 hours post-dose (dosing may occur prior to the study site visit).

All samples for pharmacokinetic analyses will be collected, identified and handled according to the laboratory manual. Exact dates and times of blood sampling, intake time of investigational medication, and whether this was taken with an accompanying meal, for the last 2 doses of investigational medication prior to the pharmacokinetic sampling must be recorded in the eCRF.

Pharmacokinetics of ARVs may also be evaluated using stored plasma samples (see Section 9.1.1), if deemed necessary and upon request of the study pharmacologist.

## 9.3.2. Analytical Procedures

Plasma concentrations of DRV, COBI and TAF of samples from subjects in the D/C/F/TAF treatment arm will be analyzed under the responsibility of the sponsor, using validated high-performance liquid chromatography-tandem mass spectroscopy (LC-MS/MS) methods.

Plasma concentrations of FTC and/or TFV of samples from subjects in the D/C/F/TAF treatment arm and plasma concentrations of the ARVs in the control arm may be determined, using validated methods, at the sponsor's discretion.

A description of the assays and validation data will be included in separate reports.

Results of bioanalyses will not be made available to the investigators.

## 9.3.3. Pharmacokinetic Parameters

Based on the individual plasma concentration-time data, using the actual dose taken and the actual intake and sampling times, the following pharmacokinetic parameters may be derived using population pharmacokinetic modeling and Bayesian feedback, if appropriate population pharmacokinetic models are available.

- Trough plasma concentration  $(C_{0h})$  and  $AUC_{tau}$  for DRV and COBI;
- Plasma concentrations x hours after dosing  $(C_{xh})$  and  $AUC_{tau}$  for TAF;
- C0h and AUCtau for FTC, TVF and their metabolites, or other ARVs in the control arm, if deemed necessary, upon request of the study pharmacologist.

# 9.4. Safety Evaluations

The study will include the following evaluations of safety and tolerability according to the time points provided in the Time and Event Schedule: AE reporting, clinical laboratory tests (including biochemistry, hematology, urinalysis, urine chemistry, and renal biomarkers), vital signs, physical examinations (complete or symptom-directed), and bone biomarkers and DXA scans of spine and hip (only for subjects participating in the substudy). These protocol procedures are described in Sections 9.4.1 through 9.4.6. In addition to these measurements, guidelines for the management of toxicities are described in Section 9.5.

Any clinically relevant abnormalities occurring at screening (from signing the ICF) and any clinically relevant changes occurring during the study must be recorded in the AE section of the eCRF.

Clinical events and clinically significant laboratory abnormalities will be graded according to the Division of AIDS (DAIDS) grading table (see Attachment 1).

Any evaluations showing abnormal results at any time during the study will be followed until satisfactory clinical resolution or stabilization. All grade 3 and grade 4 laboratory abnormalities and laboratory abnormalities resulting in an increase of 2 DAIDS grades from baseline will be followed until return to baseline or within 1 grade from baseline (ie,  $\leq$  grade 2) (for further details, see Section 9.5.1).

Any evaluations at the ESTD visit showing abnormal results indicating that there is a possible causal relationship with study drug, need to be followed by the investigator (as often as deemed prudent) until satisfactory clinical resolution or stabilization. Certain long-term AEs of ARV therapy cannot be followed to resolution within the setting of this protocol; in these cases follow-up will be the responsibility of the treating physician, which will be agreed upon with the sponsor's medical monitor.

Details regarding the Independent Data Monitoring Committee are provided in Section 11.8.

#### 9.4.1. Adverse Events

At each visit, from signing of the ICF, subjects will be asked about any untoward medical occurrences, and these will be recorded as AEs in the AE section of the eCRF. For detailed definitions and reporting procedures of AEs, please see Section 12.

Special attention will be paid to those subjects who discontinue the study for an AE, or who experience a severe AE (at least grade 3), or an SAE. For reported HIV events, further details

will be recorded if these events are AIDS-defining illnesses (see World Health Organization [WHO] Clinical Staging of HIV/AIDS, Attachment 2). For subjects experiencing specific AEs, toxicity management should be done as described in Section 9.5.

# 9.4.2. Clinical Laboratory Tests

Blood samples for biochemistry, hematology and serum pregnancy testing (females only, at screening only or if urine pregnancy test is positive), and a urine sample for urinalysis by dipstick, urine chemistry, renal biomarkers, and urine pregnancy testing (except at screening) will be collected at the time points specified in the Time and Event Schedule.

For laboratory assessments that need to be performed fasted while the subject has not fasted prior to the visit, the visit may proceed, but the subject must return within 72 hours in a fasted state to provide the necessary sample(s) for the assessments.

All clinical laboratory testing will be performed by the central laboratory and results will be sent to the investigator. The investigator must review the laboratory report, document this review, and record any clinically relevant changes occurring during the study in the adverse event section of the eCRF. The laboratory reports must be filed with the source documents.

The central laboratory will send the investigator and the sponsor an alert form whenever a grade 3 or 4 laboratory abnormality (see Attachment 1) has been observed. In case a grade 3 or grade 4 laboratory abnormality occurs, a confirmatory test should be performed preferably within 72 hours after the results have become available, before study medication interruption or discontinuation unless such delay is not consistent with good medical practice.

If a grade 3 or 4 laboratory abnormality is well documented prior to the start of the study and is not considered a safety concern by investigator, a confirmatory retest is not mandatory. The following laboratory abnormalities do not warrant mandatory confirmation:

- Asymptomatic grade 3 or grade 4 glucose elevations in subjects with pre-existing diabetes;
- Asymptomatic grade 3 or grade 4 triglyceride or cholesterol elevations.

For further details on the management of grade 3 or 4 laboratory toxicities, see Section 9.5.1 and Attachment 3.

The following tests will be performed by the central laboratory:

• Urine chemistry panel: creatinine, sodium, phosphate, glucose, protein, albumin;

(quantitative measurement).

• Urinalysis by dipstick: specific gravity, pH, glucose, protein, blood, ketones, bilirubin,

urobilinogen, nitrite, and leukocyte esterase.

If dipstick result is abnormal, urine flow cytometry will be used to analyze sediment. In case of discordance between the dipstick results and the flow cytometric results, the sediment will be examined microscopically.

In the microscopic examination, observations other than the presence of WBC, RBC and casts may also be reported by the laboratory.

- Urine renal biomarkers: RBP and beta-2-microglobulin (collected fasted).
- Cystatin C.
- AAG, ALP, AST, ALT, GGT, total bilirubin, direct and indirect Serum Chemistry panel:

bilirubin, total protein, albumin, CPK, bicarbonate, BUN, chloride, creatinine, glucose, phosphorus, potassium, sodium, uric acid, and amylase (reflex lipase testing is performed in subjects with total amylase >1.5 x ULN), and AAG.

At baseline, Weeks 24, 48, every 12 weeks following Week 48 until and including the unblinding visit, and Week 96, analyses of glucose will be done as part of the fasting metabolic assessments and not as part of the chemistry profile.

For the calculation of eGFRcreatinine according to the Cockcroft-Gault and CKD-EPI formulas, and eGFRcystatin according to the CKD-EPI formula see Section 9.5.4; the eGFR calculations will be performed by the central laboratory.

total, HDL and LDL cholesterol, triglycerides, glucose, Metabolic panel:

(collected fasted).

hemoglobin, hematocrit, RBC count and parameters (MCH, Hematology panel:

> MCH concentration and MCV), WBC count with differential (neutrophils, lymphocytes, monocytes, eosinophils, basophils),

and platelet count.

Pregnancy testing: The screening sample for biochemistry will include a serum

> pregnancy test for all female subjects of childbearing potential. A urine pregnancy test will be performed locally at all other visits. Positive urine pregnancy tests will be confirmed with a serum pregnancy test. FSH testing is required for female subjects who have stopped menstruating for at least 2 years but do not have documentation of ovarian hormonal failure. The results of the serum and urine pregnancy tests should be

recorded in the eCRF and in the subject's medical records.

• Hepatitis testing: A sample will be taken for HBV and HCV testing (HBsAg,

HCV RNA, and HCV antibody) at screening. Whenever clinically relevant, the investigator can request additional tests at

other visits.

• Bone biomarkers: CTX, P1NP and PTH and 25-hydroxy vitamin D (collected

fasted) (only for subjects participating in the bone investigation substudy). Biomarkers PTH and 25-hydroxy vitamin D should

be assessed at Day 1, Weeks 24, 48 and 96 only.

• In addition, in case of rash safety blood samples need to be taken, and are to be processed by the central laboratory. For details on rash management, see Section 9.5.2.

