### **Grade 1 and 2 Cutaneous Reaction/Rash**

A grade 1 cutaneous reaction/rash is defined as localized rash.

A grade 2 cutaneous reaction/rash is defined as diffuse rash or target lesions.

Subjects experiencing a grade 1 or 2 rash or cutaneous event may continue treatment, or have their study medication interrupted at the investigator's discretion. Safety sampling (to be processed by the central laboratory) at the time of the rash and clinical follow-up for these AEs will be at the discretion of the investigator, however, close clinical follow-up is recommended to monitor for any progression of the AE.

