#### Grade 3 and 4 Cutaneous Reaction/Rash

A grade 3 cutaneous reaction/rash is defined as:

• Diffuse rash with vesicles or limited number of bullae or superficial ulceration of mucous membrane limited to 1 site.

For the purpose of this study, the sponsor considers qualifying as a grade 3 rash:

- Cutaneous reaction/rash with at least 1 of the following:
  - elevations of ALT/AST > 2 x baseline but  $\geq$ 5 x ULN;

- fever  $\ge$ 38°C or 100°F;
- serum sickness-like reaction;
- eosinophil count >1,000/mm^3.
- The syndromes of DRESS and AGEP.

A grade 4 cutaneous reaction/rash is defined as:

- Extensive or generalized bullous lesions;
- Stevens-Johnson syndrome (SJS);
- Ulceration of mucous membrane involving at least 2 distinct mucosal sites;
- TEN.

Subjects experiencing a grade 3 or 4 rash or cutaneous event must have their study medication discontinued. Referral to a dermatologist and biopsy are required for these events preferably within 24 hours after the site becomes aware of the cutaneous event/rash.

Safety testing (to be processed by the central laboratory) of the following parameters is required to determine possible liver or systemic abnormalities: ALT, AST, bilirubin (total, direct and indirect), creatinine and a hematology profile. Close clinical follow-up and appropriate medical intervention should be instituted for these events; daily follow-up is recommended for 5 days from the onset of the event to monitor for progression of the event and weekly afterwards as long as grade 3 or 4 rash is present. Once grade 3 or 4 rash has resolved to  $\leq$  grade 2 rash, follow-up should be done according to the instructions for grade 1 or 2 rash.

Table 3: Summary of Cutaneous Reaction/Rash Follow-up

DAIDS Toxicity Grade	Definitions	Investigator Action	
Grade 1	Localized rash	Subject may continue study medication	
Grade 2	Diffuse rash	Subject may continue study	
	Target lesions	medication	
Grade 3	Diffuse rash with vesicles or limited number of bullae	Permanently discontinue study medication	
	Superficial ulcerations of mucous membrane limited to 1 site	Referral to a dermatologist and biopsy, preferably within 24 hours after the site becomes aware of the cutaneous event/rash  Laboratory assessments need to be	
	For the purpose of this protocol, the sponsor considers qualifying as a grade 3 rash the following:		
	Cutaneous reaction/rash with at least 1 of the following:	performed	

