	- Elevations in ALT and/or AST (>2 x baseline but ≥5 x ULN) - Fever ≥38°C or 100 F - Serum sickness-like reaction - Eosinophils >1,000/mm³		
	DRESS and AGEP		
Grade 4	Extensive or generalized bullous lesions SJS	Permanently discontinue study medication	
	Ulceration of mucous membrane involving at least 2 distinct mucosal sites TEN	Referral to a dermatologist and biopsy, preferably within 24 hours after the site becomes aware of the cutaneous event/rash	
		Laboratory assessments need to be performed	

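### Blood sampling for grade 1-2 rash is optional in 9.5.2, yet two of the four sponsor features that make a rash grade 3 are blood results

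*Protocol*

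**What the plan says.** Protocol 9.4.2 ends its list of central-laboratory tests with a rash item: "in case of rash safety blood samples need to be taken, and are to be processed by the central laboratory". The item carries no grade restriction and names no analytes. It then points to 9.5.2 for rash management.

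For grade 1 and 2 rash, 9.5.2 lets the subject continue study drug, or the investigator interrupt it. Safety sampling "at the time of the rash and clinical follow-up for these AEs will be at the discretion of the investigator", although "close clinical follow-up is recommended to monitor for any progression of the AE".

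For grade 3 and 4 rash, 9.5.2 states: "Safety testing (to be processed by the central laboratory) of the following parameters is required", and lists ALT, AST, bilirubin, creatinine and a hematology profile. It also states: "Subjects experiencing a grade 3 or 4 rash or cutaneous event must have their study medication discontinued".

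Beyond the skin findings, the sponsor counts a rash as grade 3 if it has any one of four features: an ALT/AST elevation, fever, a serum sickness-like reaction, or a raised eosinophil count. Table 3 gives the first as "Elevations in ALT and/or AST (>2 x baseline but ≥5 x ULN"; the text of 9.5.2 gives the last as "eosinophil count >1,000/mm" (cubic millimetre). DRESS and AGEP are a separate grade 3 item. In Table 3 the instruction "Laboratory assessments need to be performed" appears in the grade 3 and grade 4 rows only.

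**The concern.** The two sections give different sampling rules for a grade 1 or 2 rash. The order of steps in 9.5.2 is also circular: a test that can decide the grade becomes mandatory only once the grade has been assigned.

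The grade decides treatment. A grade 1 or 2 rash may stay on study drug; a grade 3 rash means permanent discontinuation, dermatology referral and biopsy. Consider a rash that is mild on the skin, without fever or a serum sickness-like reaction, in a subject whose ALT/AST or eosinophils meet the sponsor's threshold. A site that samples would stop the drug. A site that does not would continue it. Both would be following 9.5.2.

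The protocol treats this kind of reaction as relevant: section 1.2 lists DRESS, AGEP and TEN among the postmarketing reactions to darunavir, and both arms receive darunavir. At stake are subject safety and consistent handling between sites.

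**Working it through.** The plan states no figure on this point, so the check compares texts and counts.

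**Sampling rule by rash grade**

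| Grade | 9.4.2 | 9.5.2 text | Table 3 |
|---|---|---|---|
| 1 | required | investigator's discretion | not listed |
| 2 | required | investigator's discretion | not listed |
| 3 | required | required | listed |
| 4 | required | required | listed |

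Read alone, 9.4.2 requires samples at all 4 grades; Table 3 lists them at 2 of 4.

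**Features that make a rash grade 3.** There are 4: ALT/AST, fever, serum sickness-like reaction, eosinophils. Two are clinical and two (ALT/AST, eosinophils) need a blood result. The hematology profile in 9.1.2.1 includes the differential with eosinophils, so one chemistry and one hematology draw settles both.

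**The two readings**
- If 9.4.2 binds, every rash is sampled and no gap exists, but the grade 1-2 paragraph and Table 3 are wrong.
- If 9.5.2 governs, the conflict in wording goes, but 2 of the 4 features can be unmeasured when the grade is assigned.

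**What already covers the gap on the second reading**
- Scheduled draws: the Time and Event Schedule has chemistry and hematology at Weeks 2, 4, 8, 12, 24, 36 and 48. That is 7 post-baseline draws by Week 48, 4 of them by Week 12. The intervals are 2, 2, 4, 4, 12, 12 and 12 weeks. In the extension phase visits are 6 months apart, and 9.5 keeps the toxicity rules in force there.
- ALT/AST: 5 x ULN or more is at least grade 3 in Attachment 1. Any draw showing it triggers the 9.4.2 alert to investigator and sponsor. Under 9.5.1, a confirmed, clinically relevant, drug-related abnormality means withholding drug at grade 3 and permanent discontinuation at grade 4. What remains is mainly the time until the next draw.
- Eosinophils: Attachment 1 as printed has no eosinophil row, so neither the alert nor 9.5.1 grading is triggered. Detection depends on the investigator's review of the report, which 9.4.2 requires, and on a sample having been drawn.
- Discretionary measures: unscheduled safety samples (9.1.1), interruption of drug at grade 1-2, and recommended close follow-up (both 9.5.2).

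If 9.5.2 governs, none of these requires blood at rash onset.

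**Frequency.** The documents give neither a rash rate for this trial nor a rate of qualifying values in mild rash, so no expected number of subjects can be derived.

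**The case against.** The strongest reply is that 9.4.2 defers to 9.5.2. The rash item closes a list of central-laboratory tests and sends the reader to 9.5.2, the specific section, which sets sampling by grade. A site would probably follow the graded rule. Leaving blood tests for a localized or uncomplicated diffuse rash to clinical judgement is defensible, since fever, serum sickness-like reaction, vesicles or bullae, mucosal lesions, DRESS and AGEP each put the rash at grade 3 or above and so trigger testing. The investigator may also interrupt drug at grade 1-2.

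Most of this stands. A reader might infer that the protocol flatly contradicts itself and that sites cannot comply with both sections; the cross-reference makes that too strong. The reply does not remove the circularity, because the graded rule itself leaves two grade-defining results unmeasured in a rash that looks mild.

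A reader might also want two further conditions: a confirmatory ALT/AST test before a rash-related stop, and an eosinophil count read against baseline because a subject could enter with a high count. The documents do not support adding them. The 9.5.2 stop for grade 3-4 rash has no confirmation step, and the general confirmatory rule in 9.4.2 yields where delay would be poor medical practice. Inclusion criterion 12 expects hematology within normal ranges by default and admits exceptions only by a documented investigator judgement. Both conditions would loosen an unconditional safety stop.

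**Conclusion.** The point holds as a minor safety-procedure correction. Section 9.5.2 makes optional, at grade 1-2, the blood tests needed to rule out 2 of the 4 sponsor features that turn a rash into grade 3, and it differs from the sampling sentence in 9.4.2. A clinically mild rash that meets a laboratory feature can therefore stay on drug where no sample is taken, and sites can differ.

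The conclusion assumes that sites follow 9.5.2 rather than the unqualified sentence in 9.4.2, and it takes the ALT/AST threshold as printed. Existing measures cover part of the gap, more so for ALT/AST than for eosinophils. Its frequency is unknown.

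A reader might infer a bias between arms or a threat to the noninferiority result. The documents show neither: the rash rule is the same in both blinded arms, and sample size, error rate and primary analysis do not depend on it.

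**What to change.** Amend 9.5.2 and Table 3 to agree with 9.4.2:

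- In the grade 1-2 paragraph, replace discretionary sampling with a requirement such as: 'At the onset of any grade 1 or 2 rash, draw ALT, AST and a hematology profile with differential (central laboratory). If a result meets a grade 3 feature, re-grade the rash and manage it as grade 3.'
- Add the same laboratory requirement to the grade 1 and grade 2 rows of Table 3.
- State that action on a clinically evident grade 3 or 4 rash does not wait for results.
- Leave clinical follow-up of grade 1-2 rash to the investigator, and leave the ALT/AST and eosinophil thresholds unchanged.

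The cost is one protocol clarification, some extra unscheduled samples (which 9.4.2 already calls for as worded), and possibly a few more protocol-mandated discontinuations. In the Week 96 Snapshot (SAP 4.1.3), an adverse-event discontinuation before the visit window counts as non-response, so any such subjects would be counted that way. Their number cannot be estimated from the documents.
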